- bb. Adverse events are collected following signing of the informed consent form at Screening through the last study visit (FU)

CONFIDENTIAL Page 17 of 56

- cc. Perform identification and susceptibility testing at local laboratory for *Candida* for any positive blood culture or positive culture from a specimen obtained from a normally sterile site at Screening and for any positive culture requiring a change of antifungal therapy (ie, identification and susceptibility testing not required for *Candida* isolates cultured from specimens obtained on other study days without a required change in antifungal therapy).
- dd. Blood for culture must be obtained as part of the standard of care for inclusion in the study. Established mycological diagnosis of candidemia and/or IC sufficient for inclusion in the study is defined as ≥1 blood culture positive for yeast or *Candida*, a Sponsor-approved rapid IVD test positive for *Candida* spp, or a positive Gram stain for yeast or positive culture for *Candida* spp. from a specimen obtained from a normally sterile site ≤96 hours before randomization. Record species and susceptibilities for all bacteria isolated within 1 week prior to randomization from blood or any other normally sterile site. If the positive blood culture used to qualify the subject for the study is drawn >12 hours from randomization, then an additional set of blood cultures must be obtained ≤12 hours before randomization.
- ee. Obtain blood and/or normally sterile tissue/fluid for culture if demonstrating mycological eradication or if clinically indicated. Blood cultures should be repeated daily (preferred) or every other day until 2 negative blood cultures are obtained ≥12 hours apart, without an intervening positive culture. All fungal isolates cultured from blood and normally sterile tissue/fluid from Screening through the last study visit must be sent to the Central Laboratory. Record the species and susceptibilities for any new bacteria isolated from blood or any other normally sterile site.

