- ff. Obtain blood for culture at FU. If feasible, and if there was a previous culture from a site positive for *Candida* spp., obtain culture from normally sterile tissue/fluid from the same site. All fungal isolates cultured from blood and normally sterile tissue/fluid from Screening through the last study visit must be sent to the Central Laboratory. Record the species and susceptibilities for any new bacteria isolated from blood or any other normally sterile site.
- gg. Overall success for subjects with candidemia occurs if 2 blood cultures are negative and ≥12 hours apart without intervening positive blood cultures, there was no change of antifungal therapy for the treatment of candidemia, and signs attributable to candidemia at baseline have resolved; blood cultures are drawn daily until the subject qualifies as a success. Success for subjects with IC (with or without candidemia) occurs if negative culture from a normally sterile site is either documented or presumed, there was no change of antifungal therapy for the treatment of IC, and signs attributable to IC at baseline have resolved: documented mycological eradication occurs if most recent culture on or prior to the day of assessment from all normally sterile sites of baseline Candida infection (if accessible) is negative; presumed mycological eradication occurs if follow-up culture is not available (eg, normally sterile baseline site of Candida infection not accessible) in a subject with a successful clinical outcome (ie, did not receive rescue antifungal treatment and has resolution of systemic signs of IC) and resolution or improvement of any baseline radiographic abnormalities due to IC.
- hh. The Screening period for assessing systemic signs for inclusion in the study may include the 4 hours prior to the drawing of the qualifying positive blood culture (when systemic signs of infection resulted in obtaining blood cultures), qualifying positive culture from a sterile site, or qualifying rapid in vitro diagnostic, through enrollment.
- ii. On Day 5, assess presence or absence of systemic signs only (ie, not symptoms) and determine which are attributable to candidemia and/or IC
- jj. Principal Investigator to assess if the subject is a cure, indeterminate, or failure based on the criteria in Table 1-5; there is a specific electronic case report form page for completion of this assessment.

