The overall success rate is the proportion of subjects with success out of the total number of subjects evaluated.

CONFIDENTIAL Page 19 of 56

Mycological Response

Mycological response will be programmatically determined from the electronic case report form (eCRF) and central mycology data at Day 5, Day 14 (± 1 day), Day 28 (± 2 days; only for subjects with IC) and FU (Days 45-52 or Days 52-59 for subjects with IC), according to the definitions in Table 1-3. Determination of the identification of fungal pathogens will follow the process defined in SAP Section 4.

Table 1-3: Mycological Response Definitions

Mycological Response	Definition	
Success (eradication/presumed eradication) *	 If positive blood culture at baseline: The last blood culture drawn on or prior to the day of assessment and another blood culture drawn at least 12 hours prior are both negative for Candida spp and both blood cultures were drawn after initiation of study drug, AND 	
	 Any intervening blood cultures drawn between the 2 qualifying negative blood cultures are also negative for Candida spp. 	
	 If positive culture from a normally sterile site at baseline: Documented mycological eradication: culture on day of assessment from all normally sterile sites of baseline Candida infection (if accessible) is negative OR if no culture on the day of assessment, the most recent culture obtained after the initiation of study drug is negative, OR 	
	o Presumed mycological eradication: follow-up culture is not available (eg, normally sterile baseline site of Candida infection not accessible) or the most recent culture obtained after the initiation of study drug is positive in a subject with a successful clinical outcome (ie, did not receive rescue antifungal treatment and has resolution of systemic signs of invasive candidiasis that were present at baseline) and resolution or improvement of any baseline radiographic abnormalities due to invasive candidiasis,	
	 AND There was no change of antifungal therapy for the treatment of candidemia and/or invasive candidiasis, AND 	
	The subject is not lost to follow up on the day of assessment.	
	Note : Subjects with positive cultures from both blood and a normally sterile site will need to meet success criteria for both blood and normally sterile site to be considered success.	

CONFIDENTIAL Page 20 of 56

Mycological Response	Definition		

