Failure	 If positive blood culture at baseline: The last blood culture drawn on or prior to the day of assessment or any blood culture drawn prior to and within 12 hours of the last blood culture is positive for Candida spp and both blood cultures were drawn after the initiation of study drug OR The most recent blood culture drawn at least 12 hours prior to the last blood culture is positive for Candida spp. and culture was obtained after the initiation of 		
	study drug. OR If positive culture from a normally sterile site at baseline: Documented mycological persistence: culture on day of assessment from all		
	normally sterile sites of baseline Candida infection (if accessible) is positive, OR		
	o Presumed mycological persistence: follow-up culture is not available (eg, normally sterile baseline site of Candida infection not accessible) or the most recent culture obtained after the intiation of study drug is positive in a subject without a successful clinical outcome or with continued (from baseline) radiographic abnormalities due to invasive candidiasis,		
	OR • The subject requires a change of antifungal therapy to treat candidemia, OR		
	The subject dies of any cause prior to or on the day of assessment.		
Indeterminate	• If positive blood culture at baseline: A blood specimen was not available to culture or the result was not available.		
	• If positive culture from a normally sterile site at baseline: A sterile site/fluid post-baseline specimen was not available to culture or the result was not available AND an assessment of signs of invasive candiasis was not available.		
* D 1 1' .'	Subject is lost to follow-up on the day of assessment.		

^{*} Presumed eradication is defined only for a culture from a normally sterile site and is not defined for a blood culture.

Table 1-4 provides examples of timing of the blood cultures and how these are used for determination of the mycological response.

CONFIDENTIAL Page 21 of 56

Table 1-4: Examples of Timing of Blood Cultures

	Blood Cultures	Mycological Response [1]
Example 1	Day of Assessment: Day 14 (T=0 hours) Blood cultures: T=0 (N), T= -18 (N)	Success (eradication)
Example 2	Day of Assessment: Day 14 (T=0 hours) Blood cultures: T=0 (N), T=-10 (P) T=-18 (N)	Failure
Example 3	Day of Assessment: Day 14 (T=0 hours) Blood cultures: T= -20 (N), T= -28 (N) T= -34 (P)	Failure

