Example 4	Day of Assessment: Day 14 (T=0 hours) Blood cultures: T= -20 (N), T= -68 (N)	Success (eradication)

T = Time; time is relative to the date and time of assessment of mycological response.

The mycological success rate is the proportion of subjects with success (eradication/presumed eradication) out of the total number of subjects evaluated.

Clinical Response

The Investigator will make a determination of clinical response at Day 14 (±1 day), Day 28 (±2 days; only for subjects with IC), and the FU visit (Days 45-52 or Days 52-59 for subjects with IC) according to the definitions in Table 1-5. Efficacy windows are to be applied for each timepoint and are listed in Table 3-2. Subjects whose disease is progressing or who receive rescue antifungal therapy for candidemia prior to Day 14 (±1 day) will be considered a clinical failure at Day 14 (±1 day), Day 28 (±2 days; only for subjects with IC), and the FU visits. Subjects who are a clinical cure at Day 14 (±1 day) and whose symptoms recur between Day 14 (±1 day) and Day 28 (±2 days; only for subjects with IC) or FU or who receive rescue antifungal therapy will be considered a failure at the Day 28 (±2 days; only for subjects with IC) or FU visit.

CONFIDENTIAL Page 22 of 56

N = Blood culture negative for any *Candida* spp.

P = Blood culture positive for any *Candida* spp.

^[1] For Success (eradication), assumes no other criteria for failure are met.

Table 1-5: Investigator's Assessment of Clinical Response Definitions

Clinical	
Response	Definition
Cure	 Resolution of attributable systemic signs and symptoms of candidemia and/or IC that were present at baseline, AND No new systemic signs or symptoms attributable to candidemia and/or IC, AND No additional systemic antifungal therapy administered for candidemia and/or IC, AND The subject is alive.
Failure	 Progression or recurrence of attributable systemic signs or symptoms of candidemia and/or IC, OR Lack of resolution of attributable systemic signs or symptoms of candidemia and/or IC, OR Requirement for new or prolonged therapy to treat candidemia and/or IC *, OR An AE requires discontinuation of study drug therapy (IV and IV/oral) on or prior to the day of assessment, OR The subject died of any cause.

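### A subject seen at Follow-up without the scheduled blood culture can be a mycological success on two first-week negatives, and also fits the Indeterminate row with no stated precedence

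*SAP*

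**What the plan says.** Section 1.2.6.1 of the SAP derives mycological response by program at Day 5, Day 14, Day 28 (IC only) and "FU (Days 45-52 or Days 52-59 for subjects with IC), according to the definitions in Table 1-3". For a subject with a positive baseline blood culture, success needs "The last blood culture drawn on or prior to the day of assessment and another blood culture drawn at least 12 hours prior" to be negative, with nothing positive in between. The only earliest limit is that "both blood cultures were drawn after initiation of study drug". Success also requires no change of antifungal therapy for candidemia or IC, and that the subject is not lost to follow-up.

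The Indeterminate row for blood reads: "A blood specimen was not available to culture or the result was not available". It names no day or visit. A footnote to the table adds: "Presumed eradication is defined only for a culture from a normally sterile site and is not defined for a blood culture".

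Two footnotes to Table 1-1 (Section 1.2.5) govern sampling. Footnote ee says: "Blood cultures should be repeated daily (preferred) or every other day until 2 negative blood cultures are obtained ≥12 hours apart". Footnote ff says: "Obtain blood for culture at FU". The Success row does not ask for the result of that Follow-up culture.

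Section 3.10 keeps indeterminate subjects in the denominator, so they count like failures.

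**The concern.** At Day 14 a look-back is unavoidable, because sampling stops once two negatives are in hand, and the gap is at most about two weeks. At Follow-up the position differs. A blood culture is scheduled, and the visit falls well after treatment has ended. If that culture is missing, the rule falls back on negatives obtained during treatment, which show that the blood cleared on therapy. They cannot show that it stayed clear afterwards.

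Mycological and overall success at Follow-up are both secondary objectives (Section 1.1.2). Two things are at stake: whether a Follow-up mycological success means sustained clearance or only early clearance, and which of two opposite grades a programmer gives this subject.

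**Working it through.** **1. Reproduce the plan's own grades.** Read the blood part of the Success row as follows. Let t1 be the last culture at or before assessment and t2 the most recent culture at least 12 h before t1. Grade success if t1, t2 and everything between them are negative. Applied to Table 1-4 (hours relative to assessment):

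| Example | t1 | t2 | Between | Result | SAP |
|---|---|---|---|---|---|
| 1 | 0, neg | -18, neg | none | Success | Success |
| 2 | 0, neg | -18, neg | -10, pos | Failure | Failure |
| 3 | -20, neg | -34, pos (-28 is only 8 h before t1) | -28, neg | Failure | Failure |
| 4 | -20, neg | -68, neg | none | Success | Success |

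All four agree, so this is the intended reading.

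**2. Apply it at Follow-up.** Take a candidemia subject with negatives on Days 3 and 4, sampling then stopped, and a Day 45 visit without a culture. Here t1 is Day 4 and t2 is Day 3, both negative and both after the first dose. The blood rule returns success, on a culture 45 - 4 = 41 days old.

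**3. Range of the gap.** Assume the last culture falls between Day 2 and Day 7; the SAP gives no distribution.

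- Candidemia only, visit Days 45-52: 45 - 7 = 38 to 52 - 2 = 50 days.
- IC, visit Days 52-59: 52 - 7 = 45 to 59 - 2 = 57 days.
- With the Table 3-2 analysis windows (Days 38-59; IC Days 45-66): 38 - 7 = 31 to 59 - 2 = 57 days, and 45 - 7 = 38 to 66 - 2 = 64 days.

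Section 1.2.1 plans at least 14 days of treatment. In a subject who completes it, cultures up to Day 7 were taken at least a week before treatment ended.

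**4. Do the visit windows limit the look-back?** Example 4 assesses at Day 14. Its earlier culture, 68/24 = 2.8 days before, falls on Day 11 or at latest Day 12, outside the Day 13-21 window of Table 3-2, and still counts. There is no culture at the time of assessment either. The later culture is within a day of assessment, so the example does not itself show both cultures outside a window. That follows from the rule's wording, which sets no earliest date after the first dose.

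**5. The two rows side by side.** For the subject in step 2:

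- Success row: the last two cultures are negative, therapy is unchanged and the subject attended. Met.
- Indeterminate row: no blood specimen was available at this visit. Met, if the row is read as referring to the visit.

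Nothing says which is tested first. Section 3.10 grades missing responses as indeterminate, but does not settle the matter: under the Success row the response is not missing.

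**6. What the choice of row could move (illustration only).** The SAP gives no rate of missing Follow-up cultures and no planned Follow-up success rate. Borrow the 73% that Section 3.1 assumes for overall success, about 22/30 per group, and assume that 10%, 20% or 30% of these successes have no Follow-up culture. Graded Indeterminate, they leave 20/30 (66.7%), 18/30 (60.0%) or 15/30 (50.0%), against 22/30 (73.3%) if graded Success. This shows the effect of the classification choice under assumed rates. It does not estimate bias in the current rule.

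**The case against.** A reader might infer that the SAP contradicts itself, since its footnote says presumed eradication is not defined for blood. The documents do not support that. In Table 1-3, presumed eradication means inferring clearance from clinical outcome and radiology when the follow-up culture is unavailable or positive. The blood rule always needs two actual negatives after the first dose. For sterile sites, the table calls a similar look-back to the most recent negative culture documented eradication. There is no literal conflict.

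A reader might also infer that relapse goes unseen whenever the Follow-up culture is missing. That is too strong. For both endpoints, a change of antifungal therapy or loss to follow-up bars success, death from any cause is failure, and a positive culture that is one of the qualifying pair or lies between them also prevents success. Overall success further needs resolution of signs at the visit, and recurrence is failure. The investigator's clinical response at Follow-up is a separate check. What escapes is a relapse with none of these features in a subject who attended but was not cultured. The exposure is greater for mycological success, which for blood has no signs criterion.

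It can fairly be said, too, that if the Indeterminate row governs, nothing is inflated, and that Example 4 favours the Success row. But Example 4 concerns Day 14, and the SAP states no order for Follow-up. The look-back is evidently deliberate. That explains it at Day 14, where sampling has stopped by design, but not at a visit with its own scheduled culture.

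**Conclusion.** The point holds as a limited one. As written, the rule lets Follow-up mycological success for blood rest on cultures taken during treatment, and one subject can satisfy two rows with opposite consequences. Overall success at Follow-up is touched less, because of the signs criterion.

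The size is unknown. It depends on how many subjects attend Follow-up without a blood culture result, which the SAP does not give. A reader might multiply an assumed share of missing cultures by an assumed relapse rate and quote an overstatement in percentage points. Neither factor is in the document, and the second would have to be what remains after all the safeguards above. The study is descriptive and not powered for inference, and Section 3.1 expects an exact 95% interval of 53.8% to 87.5% for a 73% success rate with 30 subjects. This is a matter of clear definition and reporting. The Day 14 primary outcome is not the target.

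The statement about relapse assumes that the last culture falls in the first week and that the subject completes the planned minimum of treatment.

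**What to change.** In Table 1-3 and the Follow-up analyses (Sections 5.3.2.1 and 5.3.2.2):

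- State whether Success or Indeterminate takes precedence when a subject attends Follow-up without a blood culture result.
- Call blood eradication at Follow-up documented only if the last negative culture lies in the Table 3-2 Follow-up analysis window (Days 38-59; Days 45-66 for IC). Apply this to the last culture only; footnote ff does not ask for a second one at the visit.
- Show subjects whose success is carried forward from cultures before that window in a separate row.
- Report Follow-up mycological and overall success with and without these subjects counted as successes, keeping the denominator unchanged.

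This uses data already collected. It costs a wording change, one extra table row and a second rate, and the documented rate will be less favourable if any such subjects exist.

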Radiologic test results m																	
Blood for hematology and chemistry tests ⁿ	X		X		X			X		X						X	X
Blood for coagulation panel	X																
Urine for urinalyses, microscopy	X															X	
Urine pregnancy test °	X																X

CONFIDENTIAL Page 14 of 56

							Study 1	Drug A	Adminis	tration,	Days						FU Visit
Study Day (window) Retinal examination for	Screen	1 a	2	3	4	5	6, 7	8 ^b (±1)	9-13	14 ^b (±1)	15 ^b (±1)	16-21	22 ^{b,c} (±1)	23- 27°	28 ^{b,d} (±2)	EOT +2 days after last dose of study drug (IV and oral)	Days 45-52 for subjects with candidemia only (or Day 52- 59 for IC subjects with or without candidemia)
Candida eye infection p	X						→										
Study randomization ^q		X															
Administer IV CD101 or IV placebo		Xr	Xs	Xs	X ^t	X ^t	X ^t	X ^u	X ^t	X ^t	X ^v	Xw	X ^x	Xy	Xy		
Administer IV caspofungin or IV placebo		Xr	Xs	Xs	X ^t	X ^t	X ^t	Xu	X ^t	X ^t	Xv	Xw	X ^x	Xy	Xy		
Administer oral fluconazole or oral placebo step-down therapy if switched ^z					X ^t	X ^t	X ^t	X ^u	X ^t	X^{t}	X ^v	Xw	X ^x	Xy	Xy		
Record prior and/or concomitant medications ^{aa}	X	_													-	X	X
Record adverse events bb	X														-	X	X
Blood or normally sterile tissue/fluid for culture cc	X^{dd}	Xee	Xee	Xee	Xee	Xee	Xee	Xee	Xee	Xee	Xee	Xee	Xee	Xee	Xee	Xee	X ^{ff}
Rapid In Vitro Diagnostic Determine overall response programmatically gg	X					X				X					X		X

CONFIDENTIAL Page 15 of 56

Page 16 of 56

							Study 1	Drug A	dminis	stration,	Days						FU Visit
																	Days 45-52
																	for subjects
																EOT	with
																+2 days	
																after	only
																last	(or Day 52-
																dose of	59 for IC
																study	subjects
Ct. I. D		10	_			_		Oh	0.13	a ab	1.5h	16.01	a a h c	••	3 Oh d	drug	with or
Study Day	Screen	1 ^a	2	3	4	5	6, 7	8 ^b	9-13	14 ^b	15 ^b	16-21	22 ^{b,c}	23-		(IV and	
(window)								(±1)		(±1)	(±1)		(±1)	27 ^c	(±2)	oral)	candidemia)
Assess presence or absence																	
of systemic signs and	X^{hh}					X ⁱⁱ				X					X		X
symptoms attributable to	21					11				11					71		71
candidemia and/or IC																	
Assess for clinical response ^{jj}										X					X		X
Blood for PK testing (Part A		X	X		X			X			X						
Only) kk		Λ	Λ		Λ			Λ			Λ						

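### For a baseline-positive sterile site, SAP Table 1-3 can score a positive most recent culture as eradication while Table 1-1 footnote gg does not, and Table 1-3's own Success and Failure rows can overlap

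*SAP*

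**What the plan says.** SAP Section 1.2.6.1 derives mycological response "according to the definitions in Table 1-3". For a normally sterile site positive at baseline, that table has four relevant limbs.

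- **Documented eradication (Success):** all accessible baseline sites are negative on the assessment day, "OR if no culture on the day of assessment, the most recent culture obtained after the initiation of study drug is negative".
- **Presumed eradication (Success):** there is no follow-up culture, "or the most recent culture obtained after the initiation of study drug is positive in a subject with a successful clinical outcome", with baseline imaging abnormalities resolved or improved. As for every Success, therapy must not have been changed and the subject must not be lost to follow-up.
- **Documented persistence (Failure):** "Documented mycological persistence: culture on day of assessment from all" accessible baseline sites is positive. No clinical or imaging condition is attached.
- **Presumed persistence (Failure):** there is no follow-up culture, or the most recent one "is positive in a subject without a successful clinical outcome" or with continuing imaging abnormalities.

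Table 1-6 (exploratory response) carries the same presumed-eradication clause.

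Section 1.2.5, Table 1-1, has a row "Determine overall response programmatically gg". Its footnote gg gives a second definition for subjects with invasive candidiasis: "documented mycological eradication occurs if most recent culture on or prior to the day of assessment" is negative at all accessible baseline sites, and "presumed mycological eradication occurs if follow-up culture is not available" in a subject with clinical and imaging success. It has no branch for a positive culture.

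**The concern.** Mycological response is one of the two components of overall response in Table 1-2, and overall response at Day 14 is the primary efficacy outcome. Two passages of the same document give different answers for the same subject, and neither is marked as superseding the other. Section 7 reports no change from the protocol-defined analyses, so it does not explain the difference.

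The situation can arise. Under Table 1-1 footnote ee, post-baseline sterile-site cultures are taken only to demonstrate eradication or when clinically indicated, so an early positive culture may never be repeated.

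Timing adds to the concern. The Day 14 overall response table is in the unblinded interim set (Section 3.12), and Part A is fully unblinded before Part B is analysed (Section 3.13). A classification left to interpretation could then be settled after results are known.

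**Working it through.** **Inputs.** Table 1-3 Success and Failure rows and Table 1-2 (Section 1.2.6.1); footnote gg (Section 1.2.5); planned group sizes and the 73% success assumption (Section 3.1); the Clopper-Pearson method (Section 3.2).

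**Step 1: one baseline sterile site.** The subject is alive and not lost to follow-up, with signs resolved, imaging resolved or improved, and no therapy change.

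| Assessment-day culture | Last earlier on-drug culture | Table 1-3 Success | Table 1-3 Failure | Footnote gg |
|---|---|---|---|---|
| Negative | any | met | not met | success |
| None | negative | met | not met | success |
| None | none | met (presumed) | not met | success (presumed) |
| None | positive | met (presumed) | not met | not success |
| Positive | any | met (presumed), if read literally | met (documented persistence) | not success |

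The fourth line is a direct conflict between the two texts. The fifth is an overlap inside Table 1-3.

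**Step 2: does a narrower reading help?** Suppose the presumed limb applies only when there is no assessment-day culture. The documented limb contains that qualifier; the presumed limb does not repeat it. The fifth line then becomes Failure only and agrees with gg. The fourth line is unchanged, because it has no assessment-day culture.

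**Step 3: two baseline sites, one positive and one negative on the day, with clinical and imaging success.** Documented eradication fails because one site is positive. Documented persistence fails because it needs every accessible site positive. Presumed persistence fails because the clinical and imaging outcome is good. Presumed eradication is met only if the limb is read literally and one positive site is enough; otherwise no row applies. Footnote gg gives no success. Sites cultured on different days, one negative and the other last positive, are not addressed either.

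**Step 4: carry-through to the endpoint.** The presumed-eradication limb already requires the baseline signs to have resolved. A subject made a mycological Success by it therefore also meets the sign requirement in Table 1-2 and becomes an overall Success.

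**Step 5: size.** Clopper-Pearson limits are Beta(0.025; x, n − x + 1) and Beta(0.975; x + 1, n − x). With x = 0.73 × 30 = 21.9, these reproduce the SAP's Part A interval of 53.8% to 87.5%. In whole subjects, for an assumed number reclassified:

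| Reclassified | Successes | Rate | 95% CI |
|---|---|---|---|
| 0 | 22/30 | 73.3% | 54.1% to 87.7% |
| 1 | 21/30 | 70.0% | 50.6% to 85.3% |
| 2 | 20/30 | 66.7% | 47.2% to 82.7% |
| 3 | 19/30 | 63.3% | 43.9% to 80.1% |

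One subject moves the rate by 1/30 = 3.3 points. At the planned combined CD101 sizes it moves the rate by 1/60 = 1.7 or 1/110 = 0.9 points.

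**The case against.** **Table 1-3 is the named source.** Section 1.2.6.1 directs the programmer to Table 1-3, and Section 1.2.5 presents Table 1-1 as the schedule outlined in the protocol. Footnote gg can be read as an abbreviated schedule note. This carries weight: the likely derivation is Table 1-3. It does not settle the matter, because gg defines overall success, sits on the programmatic row, and leaves Table 1-3's internal overlap untouched.

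**The clause may be deliberate.** Presumed persistence mirrors it, and the protocol is not at hand. That stands, and it is why the choice of rule belongs to the sponsor.

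**Precedence may be implied.** Note [1] to Table 1-4 assumes that no other failure criterion is met, which suggests Failure prevails. But it is attached to blood-culture examples.

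**The mixed-site gap may not change the success rate.** Under Section 3.10, indeterminate responses stay in the denominator and count as non-successes. If unclassified subjects were handled that way, the result would match gg. The SAP does not say that they are.

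**Two stronger readings are tempting.** A reader might infer that Table 1-3 leaves an assessment-day positive unclassified. It does not: the Failure row covers it when all accessible sites are positive, and the defect is that the Success row can also be met. A reader might also infer that Table 1-3 can only raise the success rate relative to gg. That holds for the positive-culture clause alone. Elsewhere gg is looser: it does not state the exclusions for death or loss to follow-up, or that the culture must follow the start of study drug. For a subject with both blood and a sterile site positive at baseline, it tests the sterile site where Table 1-3 requires both.

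**Conclusion.** The point holds as a contradiction and an overlap in the primary-endpoint derivation. The conflict between Tables 1-3 and 1-6 and footnote gg is certain for an earlier positive culture never repeated. The double classification of an assessment-day positive depends on a literal reading of the presumed limb; the narrower reading removes it. Mixed-site results are not clearly classified. For the positive-culture clause, Table 1-3 gives Success where gg does not; no general direction of bias is claimed.

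The practical size cannot be derived from the SAP. It is zero if no subject has the pattern, and 3.3 points per subject in a group of 30. Subjects whose invasive candidiasis rests on blood culture or a rapid test plus imaging (Table 1-1 footnote c) are not reached. The rule applies equally to all arms and the study is descriptive. The Failure row of Table 1-6 is blank in the text available, so the overlap is asserted for Table 1-3 only. Severity: minor to should-fix.

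**What to change.** 1. Reconcile Tables 1-3 and 1-6 with footnote gg into one stated rule that covers an earlier positive culture never repeated, and mark which text governs.
2. Make the sterile-site Success and Failure rows mutually exclusive and exhaustive. State which row takes precedence for an assessment-day positive, and how mixed-site results are classified, whether the cultures fall on the same day or on different days. The sponsor chooses the rule.
3. Report by arm the number of successes whose most recent sterile-site culture was positive. Show Day 14 overall and mycological success under the alternative classification as a labelled sensitivity analysis.
4. Fix all of this before any remaining unblinding, at the latest Part B database lock. If Part A has already been analysed, disclose the rule that was applied.

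The cost is SAP wording, a few lines of derivation code and one extra table. The reported success rate may become slightly less favourable.
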